| D. | Aims 2 & 3 analysis | 24 |
| E. | Presentation and manuscript preparation | 25 |
| F. | Project website..... | 25 |
| G. | Public announcements..... | 25 |
| VI. Financial Policies and Procedures..... | | 26 |
| A. | General financial management | 26 |
| B. | Purchasing | 26 |
| C. | Subcontractor invoicing..... | 26 |
| D. | Participant payment | 26 |
| VII. Reporting Requirements..... | | 28 |
| A. | PCORI reporting | 28 |
| B. | Institutional reporting..... | 28 |
| C. | Risk Management and Adverse Event Reporting..... | 28 |
| D. | Research and financial misconduct | 28 |
| E. | Study completion and closeout procedures | 28 |

I. Overview

A. Project aims

The VOICe project, funded by the [Patient-Centered Outcomes Research Institute](#), will determine if group concept mapping (GCM), a structured brainstorming process, is a comprehensive and efficient method of identifying outcomes that are important to patients by comparing it to one-on-one interviews (the "gold standard"). The overarching objective of this methodology study is to provide high quality evidence to researchers, clinicians and policy makers about two methods used to elicit patient preferences for outcomes in order to inform best-practices for designing patient-centered research studies.

Aim 1: To engage patients to identify their own patient-important outcomes for managing their chronic conditions through 1) one-on-one interviews and 2) concept mapping groups.

Aim 2: To compare the comprehensiveness of concept mapping to one-on-one interviews for identifying patient-important outcomes for managing their chronic conditions.

Aim 3: To compare the efficiency of concept mapping to one-on-one interviews for identifying patient important outcomes for managing their chronic conditions.

B. Primary Outcomes

Primary outcomes:

1. Comprehensiveness of interviews as compared to one concept mapping group
2. Comprehensiveness of interviews as compared to three concept mapping groups
3. Comprehensiveness of concept mapping

Secondary outcomes: Efficiency of interviews compared to GCM

C. Timeline and key milestones

Project timeline: January 1, 2016- December 31, 2018.

- Year 1: All training and interview activities will occur during the first year of the project.
Year 2: Final interview analysis and concept mapping sessions will occur during the second year.
Year 3: Abstract preparation will and dissemination of the results will occur in the final year of the project.

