| E4 | Concept Mapping data collection | 
 • Conduct 3 sessions for each CM group (n=3CM groups, n= 60 participants) | 12/31/2017 |
| E5 | PAKSAB: CM result discussion | 
 • Discuss initial CM results | 12/31/2017 |
| E6 | Dissemination of results | 
 • Update project-specific website within Jefferson domain – include members of team, overall project goals, links to any publications (once available) | 12/31/2017 |
| E | Report Submission | Submit Progress Report, Using Interim Progress Report template | 12/31/2017 |
| F1 | Analysis Aims 2 & 3: Start | 
 • Begin assessments for Aims 2 & 3 (comprehensiveness and efficiency) | 3/31/2018 |
| F2 | PAKSAB Y3 Q1: Synthesis and reporting | 
Convene PAKSAB to complete the following:
 
 • Discuss final CM results • Prepare/submit CM abstract • Begin preparation of CM manuscript • Begin development of dissemination plan with DAT | 3/31/2018 |
| F3 | Analysis Aims 2 & 3: Finalize | 
 • Complete assessments for Aims 2 & 3 (comprehensiveness and efficiency) | 6/30/2018 |
| F4 | CM manuscript completion | 
 • Complete draft of CM manuscript | 6/30/2018 |
| F5 | PAKSAB Y3 Q2: Synthesis and reporting | 
Convene PAKSAB to complete the following:
 
 • Review CM manuscript and decide on journal for submission • Refine results for Aims 2 & 3 • Develop dissemination plan with DAT • Plan next steps planning | 6/30/2018 |

| | | | |
|----------|---|--|--|
| F7 | PAKSAB: Results delivery | 
 • Deliver CM results to PCORI • Deliver results from Aims 2& 3 to PCORI • Generate interim progress report for PCORI | 6/30/2018 |
| F | Report Submission | Submit Progress Report, Using Interim Progress Report template | 6/30/2018 |
| G1 | Abstract and manuscript for Aims 1,2 & 3 | 
 • Prepare and submit abstract for Aims 1,2 & 3 • Prepare and submit manuscript for Aims 1,2 & 3 | 9/30/2018 |
| G2 | PAKSAB Y3 Q3: Synthesis and reporting | 
Convene PAKSAB to complete the following:
 
 • Review CM manuscript • Refine results for Aims 2 & 3 • Develop dissemination plan with DAT • Plan next steps • Review manuscript for Aims 2 & 3 | 9/30/2018 |

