We will use a conventional content analysis approach for the analysis of the semi-structured interviews with the purpose of classifying the interview text into distinct categories that represent similar meanings and allowing themes to emerge from the data. [name] will oversee this analysis, and work with a coding team of four others (Project Coordinator, Research Assistant, and 2 PAKSAB members) to train them for coding interviews. The coding team will meet regularly during this process with the co-PIs to discuss codes and ideas that arise during coding.

Each transcript will be labeled with the participant's demographic and illness characteristics as well as the location along the care continuum at which the data were collected (acute, post-acute, primary care) and the mode of data collection (phone, in person). Transcripts from the same care continuum location will be analyzed together. Transcripts will be coded by members of the research team with a content analysis approach to identify thematic clusters within each set of care continuum location. Once data are coded, we will use the query function in NVivo to sort the data by various patient characteristics to examine patterns.

C. Concept mapping analysis

Data from each of the three CM groups will be entered into Concept Systems Global Software separately, with initial thematic clusters generated by the software and final clusters determined by the CM participants within each group. Each CM group will include participants from all three locations on the care continuum (acute, post-acute, primary care), thus generating three final sets of location-agnostic themes.

D. Aims 2 & 3 analysis

For Aims 2 & 3, we are comparing the comprehensiveness and efficiency of interviews and concept mapping.

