Our comparative analysis will start out with overall comparisons in which final thematic clusters from each of the three location-specific interview groups will be compared to the thematic clusters generated by the first CM group. This comparison will be a descriptive assessment of the presence/absence of each interview theme in the CM list. We will report proportions of the themes from each interview setting that were contained in the CM list as well as a detailed listing of each theme and in which lists it was present. Upon completion of this analysis, outputs from all three concept mapping groups will be aggregated and the same comparisons will be performed between the interview outcomes and the aggregated CM list.

We will then work with the RAC to study patterns in our data that emerge by setting, participant characteristics, mode of data collection, and any other categories as identified by the PAKSAB or RAC as potentially important. These analyses will be operationalized with the use of matrices and other data display techniques to study the potential contributions of these various characteristics to the outcomes identified within the proposed study. For example, a matrix of thematic clusters in columns and features of individuals (acute, post-acute, and primary care) in rows will allow us to explore consistencies and divergences in the data which are associated with these non-method based descriptors.

The efficiency of each method will be assessed by measuring overall resource utilization for conducting that method. We will determine the resource intensiveness for completion of a single concept mapping iteration through to completion, and for one set of interviews performed to saturation. The efficiency will be calculated based on the time required of research team and cost to conduct method.

We will also assess potential selection bias in who enrolled in interviews versus concept mapping using the data collected about who declines enrollment (gender, race, ethnicity, and age), and will assess on an on-going basis and at the end of the study how the enrolled patients compare to those who declined enrollment between the two groups. If we identify any systematic differences between the two groups, we will assess with our PAKSAB and our RAC how the difference(s) could have affected the thematic results obtained relative to the thematic results that we would have obtained.

E. Presentation and manuscript preparation

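### Interview themes are judged against CM group 1 and then judged again against an aggregate containing group 1, so the one-to-three-group difference could reflect changed judgements as well as added content

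*Combined protocol and SAP*

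**What the plan says.** Section V.D (Aims 2 & 3 analysis) sets two comparisons in a fixed order. In the first, the final themes from each of the three interview settings "will be compared to the thematic clusters generated by the first CM group". The measure is a judgement: "This comparison will be a descriptive assessment of the presence/absence of each interview theme in the CM list". Results are proportions by interview setting, "as well as a detailed listing of each theme and in which lists it was present". The second step follows: "Upon completion of this analysis, outputs from all three concept mapping groups will be aggregated and the same comparisons will be performed", now between the interview outcomes and the aggregated CM list.

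The two steps feed the first two primary outcomes in section I.B: "Comprehensiveness of interviews as compared to one concept mapping group" and "Comprehensiveness of interviews as compared to three concept mapping groups".

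V.D does not say who does the matching, what counts as a match, whether a second person repeats it, whether raters are masked to the CM group or to earlier calls, or whether a call made against group 1 stands when the aggregate is scored. The only coding team described is in V.B, where the lead will "work with a coding team of four others (Project Coordinator, Research Assistant, and 2 PAKSAB members) to train them for coding interviews". That concerns the interviews, not the matching for Aim 2.

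On timing, milestone E4 (section I.C) has data collection for all three CM groups due by 12/31/2017. Milestone F1 has the start of the Aims 2 and 3 assessments due by 3/31/2018.

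**The concern.** Whether an interview theme is present in a CM list is a decision about meaning. Interview themes come from content analysis by a coding team (V.B). CM clusters start in software and are settled by the participants of each group (V.C). The wording will differ, and borderline cases are to be expected.

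Under V.D, the group 1 material is judged twice, the second time with the group 1 results already complete. That opens two opposite routes to error:

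- **A more generous search.** A theme recorded as absent from group 1 is looked for again in a longer list and is accepted on the strength of a group 1 cluster that was rejected before. It then counts as a gain although groups 2 and 3 contributed nothing.
- **Anchoring.** The earlier absent call is repeated although group 2 or 3 did contain the theme. A real gain is then lost.

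A reader deciding whether one CM group is enough will compare outcomes 1 and 2 directly. The comparison also bears on Aim 3, because V.D costs a single CM iteration. It should show only what the additional groups contributed.

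**Working it through.** The plan gives no theme count, margin, test or expected proportion for comprehensiveness, so there is no figure to reproduce. The check has four steps.

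**1. Overlap of the two lists.** The first list is group 1; the second is groups 1, 2 and 3 together. With consistent matching, every theme present in the first list is present in the second, so the proportion cannot fall. A non-negative gain is built into the design and is not evidence of rater error. The difficulty is that V.D does not require consistency: no rule carries a group 1 call into the second comparison.

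**2. Weight of one changed call.** With N themes in a setting, one changed call moves the proportion by 1/N. N is an assumption, taken as 10 to 30.

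- N = 10: 1/10 = 10 points
- N = 30: 1/30 = 3.3 points

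This is the leverage of a single judgement. It does not estimate how many judgements change.

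**3. Direction, on an illustrative model.** All inputs are assumptions. Let p be the probability that a theme appears in any one CM group, with groups independent, and let f be the error rate, from 0.05 to 0.20.

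- True gain from one to three groups: [1 − (1 − p)³] − p
- Generous second pass adds f(1 − p)³
- Anchoring removes f × true gain
- Concealed list-by-list scoring with false-match rate f on every list: gain = [1 − ((1 − p)(1 − f))³] − [p + (1 − p)f]

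For p = 0.5, the true gain is 0.875 − 0.5 = 0.375. At f = 0.20, generosity adds 0.20 × 0.125 = 0.025 and anchoring removes 0.20 × 0.375 = 0.075. Concealed scoring gives (1 − 0.4³) − 0.6 = 0.336, an error of −0.039.

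Errors in percentage points, for f = 0.05 to 0.20:

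| p | True gain | Generous second pass | Anchoring | Concealed, false matches on every list |
|---|---|---|---|---|
| 0.5 | 37.5 | +0.6 to +2.5 | −1.9 to −7.5 | −0.7 to −3.9 |
| 0.7 | 27.3 | +0.1 to +0.5 | −1.4 to −5.5 | −1.1 to −4.7 |
| 0.9 | 9.9 | below +0.1 | −0.5 to −2.0 | −0.5 to −2.0 |

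The sign depends on rater behaviour that the plan does not describe. The last column shows that concealment alone does not remove matching error.

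**4. What a single matrix changes.** Score each theme once per CM group. The one-group proportion is the share of themes marked in the group 1 column; the three-group proportion is the share marked in any column. Their difference is the share of themes unmarked for group 1 and marked for group 2 or 3. Every theme counted as a gain then has an identifiable source outside group 1, and no group 1 call can change between the two outcomes.

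**The case against.** A reader might infer more than the text supports, in four ways.

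- **That scoring is unmasked and raters know the earlier calls.** V.D is silent. It names no matching raters and does not say that the same people do both comparisons. Some pages were not available for review, so a statement on rater roles elsewhere cannot be excluded. What is supported is that no masking is stated.
- **That the gain is biased upward.** Anchoring works the other way and, in the model above, has the larger effect. The direction is undetermined.
- **That a 10-point spurious gain is likely.** Two changed calls out of 20 would give 2/20 = 10 points, but nothing shows that two would change. With 20 themes and p = 0.5, about 20 × 0.125 = 2.5 themes are truly missing from all three groups, so two false finds would be 80% of them. At p = 0.7 only 20 × 0.027 = 0.5 theme is missing.
- **That the one-to-three gain is itself a primary outcome.** Section I.B names the two comparisons, not their difference, and V.D plans no test of it.

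Two further objections have weight. The promised listing of themes by list would expose a theme called absent from group 1 and present in the aggregate without a source in groups 2 or 3, provided the listing is broken down by CM group; V.D does not say that it is. And matching individual CM statements, in place of the final thematic clusters, would change the unit of the primary outcomes, so any remedy should keep the clusters. Consultation with the advisory council (V.A) is useful but is not masking.

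None of this removes the central point: the same material is judged twice, in order, with nothing tying the two sets of calls together.

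**Conclusion.** The concern holds as a risk to the comparison of primary outcomes 1 and 2, in either direction. It is not a demonstrated bias. It rests on three features of V.D: the fixed order, an aggregate that contains group 1, and the absence of any stated masking, duplicate rating or carry-forward rule. The size is unknown. The range of 3 to 10 points per changed call depends wholly on the assumed 10 to 30 themes per setting, and the modelled errors on assumed values of p and f. The change is still worth making, because it does not depend on which way judgements drift and nothing in the timeline requires group 1 to be scored ahead of the others.

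**What to change.** In V.D, replace the two sequential comparisons with one scoring pass after all three CM groups are complete:

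1. Keep the plan's unit, the final thematic clusters of each group.
2. Present the clusters from the three groups in random order, with group labels removed where feasible, and match them to the interview themes of each setting.
3. Record the matches in one theme-by-CM-group matrix, then restore the labels.
4. Take the one-group proportion from the group 1 column and the three-group proportion from the union of the three columns, with no second scoring. The same matrix serves as the promised listing.
5. If the existing coders' time allows, have two of them score independently, and report their agreement. This makes the remaining matching error visible, which concealment alone does not remove.

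The cost is a change of wording in V.D and, for step 5, a second coder's time; one pass replaces two. There are two downsides. Group 1 results are no longer available ahead of the aggregate. Concealment will be imperfect, because some team members moderate the sessions and the advisory board discusses initial CM results by 12/31/2017 (milestone E5).
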